## 7.3 Labelling

Each study drug box will be labelled with the following information:

- Sponsor identification
- Manufacturer's identification
- Protocol number
- Caution statement
- 'For Clinical Trial Use Only' statement
- Investigational product identification and batch number
- Quantity of bottles
- Storage conditions
- Expiry date

## 7.4 Storage

The investigational product will be stored in accordance with the manufacturers' instructions. Required conditions for storage will be printed on the medication label. The temperature within the load will be measured at least twice daily and recorded in the Investigator's Study File. Investigational product will be kept under adequate security by the PI and only accessible to authorised study personnel.

## 7.5 Compliance

Each subject will be dispensed sufficient medication for 24 weeks of therapy. Compliance will be checked by counting of blisters at the last visit at 6 months.

## 7.6 Accountability

The PI will maintain current record of the receipt, inventory and dispensing, including shipping invoices, of all study supplies. The Investigational Product Accountability File will include:

- Date received
- Reference number and amount received and placed in storage
- Name of study medication and dosage
- Label ID number or batch number
- Name of person responsible for each investigational product inventory entry
- Amount dispensed to and returned by each subject, including unique subject identifiers
- Non-study disposition (e.g. lost, wasted, broken)
- Amount returned to Sponsor

Accountability files will be available for inspection by the monitor at any time. Upon completion/ termination of the study, unused investigational product will be returned to the Sponsor reconciliation.

## 7.7 Concomitant and other treatments

Restricted Medication/Class of drug:	
Non-steroid anti-inflammatory drugs	
Oral anticoagulants	

Prohibited Medication/Class of drug:	
---	--

Ketoconazole/ antifungal drugs	
Clarithromycin/ antibiotics	
Ritonavir/ antiretroviral medications	
Other strong CYP3A4 inhibitors	

### 7.7.1 Other concomitant treatment

Subjects will receive a loading dose of aspirin (300 mg) prior to PCI. Unfractionated heparin will be administered during PCI in the dosage left at the discretion of interventional cardiologist. On discharge, all subjects will receive treatment with ASA 75 mg once daily, atorvastatin at least 10 mg once daily, and angiotensin-converting enzyme (ACE)-inhibitor or angiotensin II receptor antagonist (ARB). If indicated, subjects will receive treatment with  $\beta$ -receptor antagonist and mineralocorticoid-receptor antagonist.

## 7.8 Post Study Access to Study Treatment

According to the guidelines, double antiplatelet therapy with ASA and a P2Y12 receptor antagonist will be continued for 12 months. Because the study duration is 6 months, the study treatment will be continued until last visit at 6 months. After termination of the study patients will be prescribed double antiplatelet therapy for the remaining 6 months. Ticagrelor will be recommended over clopidogrel. Patients who choose to switch to clopidogrel due to financial constraints will be prescribed clopidogrel.

## 8. STATISTICAL ANALYSES

### 8.1 Statistical considerations

A single statistical analysis will be performed at the end of the study by an independent professional statistician from the Epidemiology Department of Medical University o Warsaw using IBM SPSS Statistics 20 and GraphPad Prism 5. An intention to treat (ITT) approach

will followed, i.e. statistical analysis will be based on data from all patients who were randomized and from whom meaningful data were collected. Data will be displayed graphically for visual inspection. Categorical variables will be presented as number and percent; continuous variables will be presented as mean and standard deviation (SD) or median with inter-quartile range. Shapiro–Wilk test will be used to test for non-Gaussian distribution of continuous variables.

## **8.2 Sample size**

Because there is no sufficient data to assess the impact of ticagrelor on the concentrations of PEV in patients with AMI, the SD and mean difference between the groups was estimated based on the preliminary experiments, which we conducted in during preparation for this study. The required sample size was calculated by a two-sided t-test at a significance level of 0.05 with the following assumptions: (i) SD in each group  $\pm 1$ , (ii) mean difference between the groups = 1, (iii) nominal test power = 0.9. Based on this sample size estimation, it is calculated that a total of 60 patients will be enrolled in the trial. The conference abstract [15], as well as the explanation on how the sample size has been calculated are included in Appendix E.

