#### **Principal Investigator**

**[name]**

#### **Study site(s) and number of subjects planned**

1st Chair and Department of Cardiology, Medical University of Warsaw, 60 subjects

---

Study period		Phase of development
Estimated date of first subject enrolled	28.12.2016	4
Estimated date of last subject completed	28.12.2017	4

---

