### **3.9 Discontinuation of investigational product**

The investigational product (IP) may be discontinued at any time at the discretion of the PI or the study subject. Criteria for discontinuing the investigational product include:

- Withdrawal of informed consent.
- Development of exclusion criteria, pregnancy or other safety reasons during the study (requirement of unacceptable concomitant medication, adverse event, intolerance of the IP)
- Protocol non-compliance.
- Incorrect enrolment or randomization of the subject.

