#### **3.9.1 Procedures for discontinuation of a subject from investigational product**

For subjects discontinued from the IP, the same measurements and assessments will be performed as in patients continuing the study until the last visit at 6 months, including monitoring of the adverse events. The subjects will be asked to return the study medication.

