### **3.10 Criteria for withdrawal**

Criteria for withdrawal from the study include:

- Withdrawal of informed consent.

- Development of exclusion criteria, pregnancy or other safety reasons during the study (requirement of unacceptable concomitant medication, adverse event, intolerance of the investigational product).
- Protocol non-compliance.
- Incorrect enrolment or randomization of the subject.
- Lost to the last visit at 6 months.
- Any other reason, in the investigator's opinion, that would impede the subject's participation in the study

The withdrawn subjects will be replaced by subjects subsequently recruited for the study, until the estimated sample size of the study participants will be achieved.

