#### **4.1 Enrolment/screening period**

6 months

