#### **4.2 Treatment period**

6 months

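### Section 3.10 withdraws and replaces randomised subjects without a cap, which does not fit the follow-up in 3.9.1 or the ITT approach in 8.1, and the plan does not say whether 60 means randomised or completed

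*Combined protocol and SAP*

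**What the plan says.** **Number of patients.** Section 8.2: "Based on this sample size estimation, it is calculated that a total of 60 patients will be enrolled in the trial". The synopsis lists "Medical University of Warsaw, 60 subjects". Neither place says whether 60 counts randomised or completed patients. Section 8.2 refers to Appendix E for the calculation; that appendix is not in the text available for review.

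**Withdrawal and replacement.** Section 3.10: "The withdrawn subjects will be replaced by subjects subsequently recruited for the study, until the estimated sample size" is achieved. The withdrawal criteria include "Lost to the last visit at 6 months", non-compliance with the protocol, and safety grounds that cover adverse events and intolerance of the study drug. No maximum number of replacements and no last date for them is given.

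**Stopping study drug.** Section 3.9 lists largely the same criteria, among them "Development of exclusion criteria, pregnancy or other safety reasons during the study", for stopping the drug only. Section 3.9.1 then says: "For subjects discontinued from the IP, the same measurements and assessments will be performed as in patients continuing the study", up to the 6-month visit.

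**Analysis.** Section 8.1 states an ITT approach covering all randomised patients with usable data. Section 8.3.5 compares the arms by t-test or Mann-Whitney test and names no primary time point among the three blood samplings in section 5.7.

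**Timetable.** Enrolment and treatment last 6 months each (sections 4.1 and 4.2). Section 9.3 puts first subject in at 28 December 2016, half enrolled at 28 March 2017, last subject in at 28 June 2017 and last visit at 28 December 2018. The synopsis estimates the last subject completed at 28 December 2017.

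**The concern.** A subject who stops the drug because of an adverse event, intolerance or non-compliance falls under two rules. Under 3.9.1 the subject stays in the study and is measured to 6 months. Under 3.10 the same subject is withdrawn and a new one is recruited. The plan does not say which rule governs.

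The choice affects the comparison. These reasons arise after randomisation and, in an open-label trial, may differ by arm. If 3.10 is followed, a withdrawn subject gives at most the samples taken before leaving. A later recruit then supplies the rest, so the later samplings come increasingly from people who tolerated and took their drug. That is the selection an ITT approach is meant to prevent. Replacement adds a patient; it does not recover the missing value of the one who left.

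It also affects the size of the trial. Without a definition of 60, a cap or a cut-off date, the number randomised depends on how many subjects withdraw, and recruitment has no fixed end.

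**Working it through.** **1. The plan's own figure.** Inputs from section 8.2: SD 1, difference 1, two-sided 0.05, power 0.9.

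- Normal approximation: n per arm = 2 × (1.960 + 1.282)² × (1/1)² = 21.0, taken as 22, so 44 in total.
- Exact t-test: n per arm = 22.02, so 23, or 46 in total.

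The stated inputs alone therefore do not return 60. Appendix E may hold a further allowance, so the derivation of 60 is not disputed here. What matters is that section 8.2 does not say what kind of patient the 60 counts.

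**2. Overlap of criteria.**

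| Reason | 3.9 and 3.9.1 | 3.10 |
|---|---|---|
| Adverse event, intolerance | stop drug, measure to 6 months | withdraw, replace |
| Non-compliance | stop drug, measure to 6 months | withdraw, replace |
| Loss to 6-month visit | not listed | withdraw, replace |

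**3. Number randomised if 60 must complete.** N = 60/(1 − d). The documents give no withdrawal rate, so d is an assumed range.

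- d = 5%: 60/0.95 = 63.2, so 64
- d = 10%: 60/0.90 = 66.7, so 67
- d = 20%: 60/0.80 = 75

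**4. When losses at the 6-month visit become known.** The visit table in section 4 puts the last visit at Day 168.

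- First subject: 28 December 2016 + 168 days = 14 June 2017.
- Planned enrolment: 28 December 2016 to 28 June 2017 = 182 days.
- Only subjects enrolled in the first 182 − 168 = 14 days can be found lost at that visit before enrolment closes. At an even pace (section 9.3 has half enrolled at three months) this is 14/182 × 60 = 4.6 subjects, or 7.7%.
- About 92% of replacements for this kind of loss would therefore be recruited after the planned last-subject-in date.
- The latest first-round replacement would enter on 28 June 2017 + 168 days = 13 December 2017 and reach Day 168 on 30 May 2018. That is after the synopsis completion date but before the last-visit date in section 9.3.

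**5. Power without replacement.** Section 8.2's inputs, standardised difference 1, two-sided 0.05. T-test power is from the noncentral t distribution with noncentrality √(n₁n₂/(n₁+n₂)). Mann-Whitney power is simulated on normal data (100,000 runs, standard error about 0.001). The table assumes that a lost subject drops out of the primary comparison.

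| Analysed | Noncentrality | t-test | Mann-Whitney |
|---|---|---|---|
| 30 v 30 | √15 = 3.87 | 96.8% | 95.9% |
| 24 v 24 (20% lost, even) | √12 = 3.46 | 92.4% | 90.8% |
| 30 v 20 (10 lost, one arm) | √12 = 3.46 | 92.4% | 91.0% |
| 30 v 18 (12 lost, one arm) | √11.25 = 3.35 | 90.7% | 88.8% |

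**The case against.** The strongest reply is that the passages can be reconciled. Section 3.10 refills to the estimated sample size, section 8.2 gives that size as 60, and the synopsis calls it planned, so 60 can be read as a net target. That stands: a reader might infer that 3.10 and 8.2 cannot both hold, and the documents do not support this. They leave the meaning of 60 undefined.

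Other stronger readings also go too far:

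- **That late replacement must breach the timetable.** The synopsis dates are labelled as estimates, and the last-visit date in 9.3 would let late replacements finish. But that date conflicts with the synopsis by a year, and it does not change the planned last-subject-in date. The ±6-month window for Visit 5 adds nothing, because the visit and day columns of that table do not line up as read.
- **That nearly all replacements come late.** This is shown only for losses at the 6-month visit. If withdrawal times were uniform over 168 days, about 84/182 = 46% of replacements for earlier withdrawals would fall after enrolment closes.
- **That withdrawn subjects are certain to be left out of the analysis.** Section 8.1 covers any randomised patient with usable data, and no section says that a replacement takes over a withdrawn subject's place. The shift towards completers follows if 3.10 is applied and measurement stops.
- **That 24 per arm is the number that will be analysed.** Section 8.3.5 names no primary time point, and a subject lost at 6 months may still have given the first two samples.

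Replacement with a cap and a cut-off date, keeping everyone in the ITT set, would also close the number. It would still need 3.9.1 and 3.10 to be reconciled, and would add patients.

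**Conclusion.** The point holds as a conflict of rules with a consequence for bias. Section 3.10, followed as written, withdraws randomised subjects for possibly arm-related reasons and refills with later recruits. Sections 3.9.1 and 8.1 already support the less biased rule of following them and analysing them as randomised. The number randomised is open: 64 to 75 over the assumed 5% to 20% withdrawal, if 60 means completed. For losses at the 6-month visit alone, about 92% of replacements would be recruited after 28 June 2017, assuming even enrolment, the Day 168 visit and the estimated dates.

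On section 8.2's inputs, replacement is not needed to keep 0.9 power at 20% evenly split loss. If 12 losses all fell in one arm, Mann-Whitney power would be slightly below 0.9. These figures rest on normal data and a 1 SD difference. The plan should be changed, but the point does not show that 60 is the wrong number.

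**What to change.** - **Section 3.10:** state that randomised subjects are not replaced and that, unless consent is withdrawn, they are measured to the 6-month visit as in 3.9.1 and analysed as randomised under 8.1.
- **Section 8.2:** state that 60 is the number randomised, 30 per arm.
- **If Appendix E defines 60 as completed patients:** say so in 8.2 and align 4.1, 9.3 and the synopsis number with it.
- **In either case:** reconcile the last-visit date in 9.3 with the completion date in the synopsis.

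The change to the rule takes one sentence in 3.10 and one in 8.2, and no patients beyond 60. The price is some power. If losses leave the primary comparison, 20% evenly split loss lowers it from about 97% to 92% by t-test, or from 96% to 91% by Mann-Whitney. The 30 against 18 case gives about 91% or 89%.

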## **8.3 Definitions of analysis sets**

The following sets of analysis will be performed: analysis of baseline characteristics, efficacy analysis, PRO analysis.

### **8.3.1 Efficacy analysis set**

The efficacy of ticagrelor will be assessed as decrease in concentration of PEVs (flow cytometry), in comparison with clopidogrel.

### **8.3.2 Safety analysis set**

AE reported throughout the course of the study including pre-study, study and post-study findings of physical examination, vital signs, laboratory variables, and 12-lead ECG will be listed individually per treatment group and analyzed. Due to the fact that the study is not

powered for clinical endpoints, AE will be analyzed as safety events and reported descriptively.

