### 2.3 Safety objectives

Safety Objective:	Outcome Measure :
To evaluate the safety and tolerability of ticagrelor in relation to clopidogrel. To be reported descriptively.	

- Vital signs

- Abnormal values in blood tests ( haematology and clinical chemistry)

- Abnormal values or in urinalysis

- Abnormalities in 12-lead ECG

- AEs/ SAEs

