## 3. SUBJECT SELECTION, ENROLMENT, RANDOMISATION, RESTRICTIONS, DISCONTINUATION AND WITHDRAWAL

### 3.1 Inclusion criteria

- Age > 18 years
- Informed consent to participate in the study
- PCI due to first ST-elevation myocardial infarction (STEMI) or non-STEMI (NSTEMI)
- Administration of the loading dose of clopidogrel (600 mg) prior to PCI

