#### **4.3 Follow-up period**

No follow-up period after the end of the study treatment.

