## **6. SAFETY REPORTING AND MEDICAL MANAGEMENT**

### **6.1 Definition of adverse events**

Adverse events (AE) and serious adverse events (SAE) will be defined according to the guidelines of Food and Drug Association. AE will be defined as the development of an undesirable medical condition or the deterioration of a pre-existing medical condition occurring during the study in a subject administered a pharmaceutical product which does not necessarily has a causal relationship with the product. SAE will be defined as any AE which fulfil one or more of the following criteria:

- Results in death;
- Is immediately life-threatening;
- Requires hospitalization;
- Results in persistent or significant disability or incapacity.
- Is a congenital anomaly/ birth defect.

The following hospitalisations will not be considered to be SAE:

- Those planned before entry into the study;
- Elective treatment for a condition unrelated to study indication or study treatment;
- Occurred on an emergency outpatient basis and do not result in admission (unless fulfilling other criteria in SAE definition);
- Part of normal treatment or monitoring of the study indication and are not associated with any deterioration in condition.

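### Section 8.3.2 puts pre-study findings among the AEs compared by arm, and the abnormal-value outcomes in 2.3 have no baseline reference, so abnormalities present before randomisation can dilute the safety summaries

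*Combined protocol and SAP*

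**What the plan says.** Section 2.3 lists five safety outcome measures. Three of them are abnormal findings: in blood tests, in urinalysis and on the ECG, the last given simply as "Abnormalities in 12-lead ECG". None has a limit, a grade or a comparison with the patient's own earlier value.

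Section 8.3.2 is the only section on the safety analysis. It covers "AE reported throughout the course of the study including pre-study, study and post-study findings of physical examination, vital signs, laboratory variables, and 12-lead ECG". These "will be listed individually per treatment group and analyzed", and "AE will be analyzed as safety events and reported descriptively". Section 8.1 presents categorical variables as number and percent.

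Other sections set the time frame differently:

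- Section 6.1 defines an AE as "the development of an undesirable medical condition or the deterioration of a pre-existing medical condition occurring during the study".
- The schedule in Section 4 has no AE review at Visit 1. AE review begins at the visit where randomisation takes place.
- The section on the time period for collecting AEs names the visits of the index hospitalisation and the 6-month visit.
- Section 4.3 states: "No follow-up period after the end of the study treatment".

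Under 3.1 every patient has had PCI for a first STEMI or NSTEMI. Visit 1 (window Day −1 to 0) includes ECG, vital signs, haematology, clinical chemistry and urinalysis. No section defines a treatment-emergent finding, a change from baseline or a shift table.

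**The concern.** A finding that exists before randomisation cannot be an effect of the allocated drug. It carries no information about the difference between the arms, yet 8.3.2 places it in the by-arm safety material, and the wording of 2.3 gives no ground for removing it. The population makes this more than a formality. The qualifying event is an acute infarction, Visit 1 falls within a day of it, and 5.2.3 has the ECG report cover the QRS complex, ST segment and T wave.

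Two things are at stake. First, a count of patients with any abnormality moves both arms towards the same high figure and understates a real difference in tolerability. Second, the AE rule is open: one analyst following 6.1 and another following 8.3.2 could produce different AE tables from the same data, and the choice could be made after the results are seen. Safety is a stated objective and no test is planned, so the displayed counts are themselves the result.

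**Working it through.** **Step 1. The sections side by side.**

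| Finding | Section 8.3.2 | Other sections |
|---|---|---|
| Present before randomisation, unchanged | Included (pre-study) | Not an AE under 6.1; no AE review at Visit 1 |
| New or worse between randomisation and the 6-month visit | Included | AE under 6.1; reviewed from the randomisation visit |
| After the last visit | Included, if post-study means this | Not collected: 4.3 and the AE collection period |

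The definition in 6.1 governs AEs. It does not govern the separate abnormal-value outcomes in 2.3, which have no baseline rule anywhere.

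**Step 2. Inputs for the size.** The plan gives no safety figure to reproduce. The only number taken from it is the arm size: 60 patients (8.2) at 1:1 (3.3), so 30 per arm. Everything else is an assumption:

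- b, the share abnormal before randomisation, taken as equal in both arms, from 0 to 90%.
- p, the probability of a new abnormality after randomisation, independent of baseline status: 5% in one arm and 30% in the other.

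**Step 3. Formula.** A patient counts as having any abnormality if abnormal at baseline, or if not and newly abnormal later:

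P(any) = b + (1 − b)p

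Difference between arms = (1 − b)(p₂ − p₁)

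A new-or-worsened count has the difference p₂ − p₁, whatever b is.

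**Step 4. Results for 5% and 30%.** For example, at b = 50% the two arms are 0.5 + 0.5 × 0.05 = 52.5% and 0.5 + 0.5 × 0.30 = 65%, a difference of 12.5 points.

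| b | Expected patients of 30, any abnormality | Difference (points) | Ratio |
|---|---|---|---|
| 0 (same as counting only new findings) | 1.5 and 9.0 | 25 | 6.0 |
| 25% | 8.6 and 14.2 | 18.8 | 1.65 |
| 50% | 15.8 and 19.5 | 12.5 | 1.24 |
| 75% | 22.9 and 24.8 | 6.3 | 1.08 |
| 90% | 27.2 and 27.9 | 2.5 | 1.03 |

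**Step 5. Other assumed rates.** The factor is the same. For 5% and 20% the 15-point difference becomes 7.5 at b = 50% and 1.5 at b = 90%. For 5% and 40% the 35-point difference becomes 17.5 and 3.5.

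**Step 6. Chance imbalance.** With b = 50% and independent patients, the standard deviation of the difference in baseline-abnormal counts between two arms of 30 is √(2 × 30 × 0.5 × 0.5) = 3.9 patients, or 3.9/30 = 13 points. Most of such an imbalance carries into an any-abnormality count, where it has nothing to do with treatment.

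**The case against.** The strongest reply is that no section prescribes a per-patient any-abnormality count. Section 8.3.2 promises individual listings and descriptive reporting. The collected data also separate old findings from new: Visit 1 values, AE start and stop times, causality assessments and a question about problems since the previous visit. Section 6.1 already excludes a stable infarct-related ECG change from the AEs, and 8.3 plans an analysis of baseline characteristics. Post-study may mean no more than the examination at the final visit.

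Much of this stands. The information is recoverable, and the dilution touches summary counts of abnormal values rather than AEs and SAEs classified under 6.1. But listings do not supply a counting rule, 8.3.2 says the findings will also be analysed, and the default display in 8.1 is number and percent. On post-study, one wording query is enough.

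A reader might go further and infer that the infarction fills both arms and hides drug effects. The documents do not support that:

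- They give no baseline abnormality rate, so the size is unknown.
- They do not show that every patient's Visit 1 ECG is abnormal. NSTEMI patients are eligible, the STEMI share is not given, and nothing says that the Visit 1 ECG precedes PCI.
- They give no reason to expect the infarction to dominate every laboratory or urine item. The panel includes haemoglobin, platelets, creatinine, sodium and potassium.
- In expectation the dilution favours neither arm.

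**Conclusion.** The point holds as a defect of definition with a possible, unquantified effect on the safety summaries. Section 8.3.2 conflicts with 6.1, the schedule and 4.3, and the abnormal-value outcomes in 2.3 lack a baseline reference. If findings are tabulated as any abnormality, the arm difference shrinks by (1 − b): from 25 points to between 18.8 (b = 25%) and 2.5 (b = 90%) under assumed rates of 5% and 30%. Those rates, the values of b, equal b in both arms and independence of p from baseline status are all assumptions. Only the factor (1 − b) follows from the way of counting.

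Safety is descriptive, no safety test or decision rule depends on these counts, and the primary comparison of PEV concentrations is untouched. It should be corrected before the safety tables are produced, but it does not threaten the trial's main conclusion.

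**What to change.** 1. In 2.3 and 8.3.2, summarise ECG, laboratory, urinalysis and vital-sign findings as new or worsened relative to the last pre-randomisation (Visit 1) value, with shift tables by arm and visit. Vital signs are also scheduled at the randomisation visit, so state which reading is the baseline.
2. In 8.3.2, count as AEs only events with onset or worsening after randomisation and up to the last visit, in line with 6.1. Randomisation is a clearer starting point than the first dose of randomised drug, because control patients continue a drug they have already started.
3. Move pre-study findings to the analysis of baseline characteristics in 8.3.
4. Delete the post-study wording or reconcile it with 4.3. If it means the 6-month visit, say so.

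The cost is protocol wording and a set of shift tables. The Visit 1 measurements are already scheduled, so no new data are needed.

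One limit remains. ECG and laboratory changes that evolve from the infarct after Visit 1 will still count as new or worsened in both arms. The rule removes what was present before randomisation and cannot remove the later course of the disease.
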